Date: November 11, 2025

Study Title: Enhancing Treatment of Hoarding Disorder With Personalized In-Home Sorting and Decluttering Practice

NCT02843308

Scientific background:

Hoarding disorder (HD) is characterized by persistent difficulties parting with possessions, associated distress, and clutter that compromises the intended use of living spaces (American Psychiatric Association, 2022). HD is common, with an estimated overall pooled prevalence of 2.5% of the general population (Postlethwaite et al., 2019). HD causes significant impacts on social, occupational, and other important areas of functioning and health risks include falls and other injuries due to clutter (American Psychiatric Association, 2022). In severe cases, home fires and pest infestation extend health and safety risks to neighbors (Frost et al., 2000). HD is associated with significantly lower quality of life, social isolation, and high rate of co-occurring mental disorders (Frost et al., 2011a; Ong et al., 2015; Saxena et al., 2011; Tolin et al., 2019). Cognitive behavioral therapy (CBT) for hoarding symptoms has shown promise when delivered by a trained therapist in either individual or group settings (Tolin et al., 2015); however, cost and access to a therapist may be barriers for some (Thompson et al., 2017). One alternative is the Buried in Treasures [BIT] Workshop, an evidence-based, highly structured, short-term, skills-based group using CBT principles but led by peers (Frost et al., 2012a) or non-professional facilitators (Frost et al., 2011a). To date, studies have shown BIT can significantly reduce hoarding symptoms when compared to a waitlist control (Frost et al., 2012a) and is as effective as psychologist-led group CBT (Mathews et al., 2016). Despite these promising results, many continue to have impairing symptoms after treatment and high levels of clutter, regardless of modality or type of facilitator (Moulding et al., 2017; Tolin et al., 2015) and under-utilize HD treatments and services (Frost et al., 2012b). Approaches that enhance the clinical effects of these interventions are needed. Based on two studies—one reporting that personalized care and accountability made treatments more acceptable to individuals with hoarding disorder (Rodriguez et al., 2016) and another reporting that greater number of home sessions were associated with better clinical outcomes (Tolin et al., 2015)—we tested the feasibility and effectiveness of adding personalized, in-home uncluttering sessions to the final weeks of BIT with up to 20 hours of supervised in-home uncluttering practices in a small (N = 5) pilot study of BIT+ (Linkovski et al., 2018). Reductions in hoarding symptoms, clutter, and impairment of daily activities were observed. Treatment response rate was comparable to rates in other BIT studies, with continued improvement in clutter level after in-home uncluttering sessions (Linkovski et al., 2018). Although the pilot study of BIT+ was promising, it had limitations including the small sample size and open-label design. To build upon this small pilot, we tested BIT+ in a larger sample using a randomized waitlist-controlled trial design and hypothesized that individuals randomized to BIT+ would have more significant and more substantial benefits on hoarding symptoms than patients randomized to an 18-week long waitlist. After the waitlist, participants were offered BIT+, and the BIT+ completer sample was pooled to allow us sufficient sample size to estimate clinical benefits.

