
Objectives:

To test BIT+ in a larger sample using a randomized waitlist-controlled trial design; we hypothesize that individuals randomized to BIT+ will have more significant and more substantial benefits on hoarding symptoms than patients randomized to an 18-week long waitlist.

Design:

This randomized waitlist-controlled trial with 1:1 (BIT+ intervention; waitlist control) allocation was conducted at an academic outpatient research setting. Potential participants were recruited via study advertisements posted online and in the local community, radio ads, and by referrals from mental health professionals and local hoarding task forces between October 2016 and June 2019. The study protocol was approved by the Stanford Institutional Review Board (IRB), and participants provided written informed consent. The trial was prospectively registered; clinicaltrials.gov identifier: NCT02843308. Participants were randomized by group, employing random permuted blocks within a 1:1 allocation ratio between intervention and waitlist control groups. The group therapy facilitators could not be blinded to allocation for practical reasons; the independent evaluators who assessed home clutter levels were blinded to allocation. Although several trial designs (with an active comparator) were considered, limited resources prohibited these options. A waitlist-controlled trial design was selected given treatment could be delivered to all participants, while controlling for passage of time and allowing comparison to a prior study of BIT that also employed a waitlist control condition (Frost et al., 2012a).

Methods:

a) Inclusion and Exclusion Criteria

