We will employ standard linear mixed effects modeling (e.g., Bryk and Raudenbush, 2002; Singer and Willett, 2003) to estimate and compare the change from the pre-to post-treatment assessment during the first segment of our study in line with the intention to treat principle. The use of mixed effects modeling was chosen because this approach is better at handling missing data and yields improved power compared to linear regression. Specifically, we used a random intercept model assuming linear change. We will use maximum likelihood estimation with robust standard errors implemented in Mplus Version 8.4 (Muthén & Muthén, 1998–2017). Data points that are missing due to subject attrition will be handled assuming that data are missing at random (MAR; Little and Rubin, 2019) conditional on observed information. In our mixed effects analyses, the change (slope) in the outcome will be modeled as the key dependent variable predicted by the treatment assignment status. In particular, the change in SI-R total from baseline to end of treatment will be assessed. Specifically, will report the number of participants who met and exceeded the response criteria of the SI-R total (SI-R reduction ≥ 14 points).

In all analyses, we will use the nominal significance level ($\alpha = 0.05$). We will not adjust the significance level for multiple testing given that we had one clear primary endpoint. We will analyze several secondary outcomes including subscales of SI-R. We applied the same analytical strategy to analyze the data from the second segment of our study, where the individuals assigned to the waitlist condition

receives BIT+. Additionally, we will compare the first and second segments in terms of the estimated changes under BIT+ treatment.

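### The plan uses robust maximum likelihood at 0.05 with no small-sample correction and no stated sample size; with a normal reference, type I error would be about 0.055 to 0.069 at 50 down to 15 per arm

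*Combined protocol and SAP*

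**What the plan says.** The Statistical Plan compares change from pre- to post-treatment between BIT+ and waitlist in a mixed model: "we used a random intercept model assuming linear change". The quantity of interest is stated as "the change in SI-R total from baseline to end of treatment will be assessed". On estimation it says: "We will use maximum likelihood estimation with robust standard errors implemented in Mplus Version 8.4". On the error rate it says "In all analyses, we will use the nominal significance level", given as 0.05, with no multiplicity adjustment because there is one primary endpoint. The same strategy is applied to the second segment, in which former waitlist participants receive BIT+, and the two segments are then compared.

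The plan does not mention restricted maximum likelihood, a t or F reference, degrees of freedom, a small-sample correction to the robust standard errors, or whether tests are two-sided. No sample size, power or expected dropout appears anywhere in the document. The only count given is the pilot's N = 5, and this trial is described only as larger than that.

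**The concern.** Maximum likelihood with a sandwich variance is justified as the number of independent units grows. In finite samples two things push the same way. The variance estimate divides by n where n − 1 would be unbiased, so the standard error is too small. If the ratio is then compared with 1.96, the cut-off ignores the uncertainty in that standard error. Intervals come out too narrow and the test rejects a true null hypothesis more than 5% of the time.

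At stake is whether the stated 0.05 is achieved for the single primary endpoint, on which the plan relies when it declines to adjust for multiplicity. The second segment is more exposed because it has only one arm, which can hold no more people than were randomized to waitlist.

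**Working it through.** **Inputs**
- Estimator, model and contrast: Statistical Plan, as quoted above.
- Alpha: 0.05 (Statistical Plan). Two-sided testing is assumed.
- Allocation: "random permuted blocks within a 1:1 allocation ratio" (Design), so n per arm is taken as equal.
- n per arm: not stated; shown over a range.
- Reference distribution: not stated; normal assumed.

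**The plan's own figure.** As n grows, the cut-off 1.960 gives exactly 0.05, so the nominal level is reproduced in the large-sample limit.

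**Two-arm primary contrast.** With both assessments observed for everyone and arms free to differ at baseline, the treatment-by-time estimate is the difference in mean change. Each arm contributes Σ(residual change)²/n² = [(n − 1)/n] × s²/n to the sandwich variance. The standard error is therefore √((n − 1)/n) times the unbiased one. Under normality, equal variances and independent participants:

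type I error = 2 × P( t with 2n − 2 df > 1.96 × √((n − 1)/n) )

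width ratio = 1.96 × √((n − 1)/n) ÷ t(0.975; 2n − 2)

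For n = 20: √(19/20) = 0.9747; 1.96 × 0.9747 = 1.910; the correct quantile on 38 df is 2.024. The type I error is 0.0637 and the width ratio is 1.910/2.024 = 0.944.

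| n per arm | type I error | 95% interval width relative to correct |
|---|---|---|
| 10 | 0.079 | 0.885 |
| 15 | 0.069 | 0.924 |
| 20 | 0.064 | 0.944 |
| 25 | 0.061 | 0.955 |
| 30 | 0.059 | 0.963 |
| 50 | 0.055 | 0.978 |
| 100 | 0.053 | 0.989 |

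**Single-arm second segment.** The same formula with n − 1 df gives 0.079 at n = 15, 0.071 at 20 and 0.064 at 30.

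**Simulation check.** Random-intercept maximum likelihood with a sandwich standard error was simulated with an assumed within-person correlation of 0.6 and 3,000 replicates (Monte Carlo standard error about 0.4 to 0.6 points).
- Complete data: 0.080, 0.065, 0.064 and 0.059 at 10, 15, 20 and 30 per arm, in line with the formula.
- Assumed 20% dropout, missing at random: 0.106, 0.073, 0.067 and 0.060.
- At 50 per arm: 0.063 with complete data and 0.052 with dropout, against an exact complete-data value of 0.055. These runs are too noisy to resolve so small an excess, so the formula is preferred there.
- Arms constrained to a common baseline mean, complete data: 0.088, 0.073, 0.060 and 0.062 at 10, 15, 20 and 30 per arm. The result does not hinge on that modelling choice.
- Model-based maximum likelihood standard errors give nearly the same rates (0.081 against 0.080 at 10 per arm). The problem is the uncorrected variance with a normal cut-off, not robustness as such.

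**With the correction.** An unbiased variance and a t reference on 2n − 2 df give exactly 0.05 at every n in the same complete-data, equal-variance case.

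**The case against.** Much of the case on the other side stands.

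- **Size of the trial.** A reader might infer from the Scientific background that the randomized arms are known to be small, since "the BIT+ completer sample was pooled to allow us sufficient sample size to estimate clinical benefits". That sentence concerns a completer estimate of benefit made after the waitlist period. It does not give the size of the randomized comparison. Limited resources, the 30-mile limit and repeated home visits suggest modest numbers but do not establish any.
- **The normal cut-off.** It is inferred from the named method. The plan gives no reference distribution, so it cannot be said to have specified 1.96.
- **Magnitude.** The excess is 0.5 to 1.9 percentage points over 50 down to 15 per arm, and about 1 point at 25 to 30. Larger figures need very small arms, dropout that the plan does not quantify, or the non-randomized second segment.
- **Therapy groups.** Participants were randomized by group and the model has no group term. With assumed groups of 5 to 10, 20 to 30 per arm and intraclass correlations of 0.02 to 0.10, simulated type I error with participant-level standard errors was about 0.075 to 0.19. That could outweigh the present point. It does not remove it: adding a group term while keeping uncorrected inference would leave a small-sample bias, then governed by the number of groups.
- **A simple switch to restricted maximum likelihood can lose robustness.** With a common residual variance it assumes equal change variance in treated and waitlist arms. In simulations of change scores with 22 and 30 completers and an SD ratio of 1.5 (larger in the smaller arm), the pooled t test gave 0.065 against 0.063 for the planned robust test. With a ratio of 2 the figures were 0.076 and 0.065. With 15 and 20 completers and a ratio of 2 they were 0.075 and 0.072. With equal arms of 20 and a ratio of 1.5, pooling did work: 0.051 against 0.065. An unequal-variance t analysis held 0.050 in every case tried. This objection stands and shapes the fix.
- **Timing.** Recruitment ended in June 2019, the document is dated November 2025, and parts of the plan are in the past tense. The remedy may have to be a reanalysis.

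**Conclusion.** The point holds as a conditional one. The plan pairs a large-sample method with a 0.05 level and gives neither a sample size nor a small-sample safeguard, so a reader cannot tell whether 0.05 is achieved. If a normal reference is used, the error is always in the liberal direction under complete data, equal variances and independent participants. It is about 0.06 at 20 to 30 per arm, above 0.07 only below about 15 per arm, and close to nominal from 50 per arm. The second segment runs somewhat higher at the same n.

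The documents do not support the stronger statement that this is a small trial whose type I error is materially out of control. N is not given, the reference distribution is not stated, and the calculated excess would change a conclusion only when the result is borderline. The correction is still worth making because it is cheap and bears on the only primary endpoint.

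**What to change.** State the number randomized and analysed in each arm and segment. Then replace the estimation sentence with wording such as: *Robust standard errors will be computed with a bias-reduced small-sample correction; tests and intervals will use the t distribution with Satterthwaite-type degrees of freedom.* An acceptable alternative is restricted maximum likelihood with arm-specific variances and Kenward-Roger or Satterthwaite degrees of freedom. Common-variance restricted maximum likelihood should not be the replacement. State that tests are two-sided, if that is intended. Apply the same inference to the first segment, the second segment and the comparison between them.

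If the analysis has already been run, report the corrected inference alongside the original results.

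Cost: a refit outside the named software and slightly wider intervals. Taking the reciprocals of the width ratios, these are about 8% wider at 15 per arm (1/0.924 = 1.08), 6% at 20 (1/0.944 = 1.06), 4% at 30 (1/0.963 = 1.04) and 2% at 50 (1/0.978 = 1.02). No new data are needed.

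This does not deal with correlation within therapy groups. If a group term or group-level clustering is added, the correction and the degrees of freedom should be set at that level.
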